### 4.3.2 Handling of Participant Withdrawals or Termination

If a subject is removed or withdraws from the study, the date and reason for withdrawal will be recorded on the appropriate electronic case report form (eCRF). If the subject is withdrawn due to an adverse event (AE) or serious adverse event (SAE), the Investigator should follow the subject until the AE/SAE has resolved or is considered stable.

If a subject is unable to return for an office/clinic visit or cannot be contacted by telephone, 3 separate telephone calls should be made to obtain subject related safety information. All attempts should be documented in the source documents. If the subject does not respond to the 3 telephone calls, then the investigator must send a certified letter to the subject. If the subject does not respond to the letter, then the subject will be considered “lost to follow-up” for the study.

Subjects who have signed the ICF, but are later found not to be eligible PRIOR to insertion of the study catheter can be replaced. Replacement subjects will be recruited and enrolled following the same procedures as non-replacement subjects.

## 4.4 Subject Enrollment Disposition

- **Enrolled Subjects:** Patients who sign the informed consent form.
- **Evaluable Subjects:** All enrolled subjects who have the study catheter inserted.
- **Excluded Subjects:** Subjects who are enrolled but never undergo insertion of the study catheter. Excluded subjects will only be followed between ICF signature and exclusion for event reporting.
- **Roll-In Subjects:** Enrolled Subjects who have the study catheter inserted and RF delivered during the roll-In phase of the ablating investigator. These subjects will not be included in the main study analyses and will be analyzed separately.
- **Discontinued Subjects:** Enrolled subjects who have the study catheter inserted but do not undergo ablation (i.e., no RF energy is delivered with the study catheter). Discontinued subjects will remain in follow-up for 30 days.
- **Lost to Follow-up Subjects:** Evaluable subjects of which contact is lost after most recent visit (despite 3 documented attempts to contact the subject).
- **Withdrawn / Early Termination Subjects:** Subjects who withdraw consent for study participation or are withdrawn by the investigator, are terminated from the study prior to completion of all follow-up visits.
- **Completed Subjects:** Enrolled subjects who have not been excluded, discontinued, withdrawn, terminated early, or lost-to-follow-up from the study prior to the final study visit.

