### 1.2.3 The RADIANCE Clinical Investigation

A first in human 'RADIANCE' study with the Multi-electrode RF Balloon Catheter enrolled subjects between December 2, 2016 and March 8, 2017 in Europe. In this feasibility study 40 subjects with paroxysmal atrial fibrillation were enrolled. One subject (7.1%) was excluded prior to RF ablation procedure. In total 39 subjects were treated with the investigational Biosense Webster multi-electrode RF balloon catheter. Four different centers with 9 different operators participated in the study.

Of the 40 enrolled subjects, 23 (57.5%) were male and 17 (42.5%) were female. The mean age for the 40 subjects was  $60.7 \pm 10.02$  years. The most prevalent medical condition reported at baseline was (systemic) hypertension (22/40 (55.0%)). Subjects suffered from symptomatic AF for an average of  $51.7 \pm 49.71$  months at baseline.

The primary endpoint was the incidence of primary procedure-related adverse events occurring within seven days of the procedure. From the primary safety endpoint, one subject (2.5%) experienced an early-onset (<7 days) primary adverse event, Diaphragmatic Paralysis. No subject deaths, atrio-esophageal fistula, myocardial infarction, cardiac tamponade/perforation, heart block, thromboembolism, CVA, TIA, pneumothorax, pulmonary edema, pericarditis, major vascular access complication/bleeding, moderate or severe pulmonary vein stenosis were reported.

Apart from the primary adverse events, there were 4 serious adverse events (SAE) reported as not being related to the investigational device and study procedure. One SAE (prolonged hospital stay for esophageal erythema) has been reported as possibly device and definitely (causal relationship) procedure related.

Among 39 subjects that underwent post-ablation cerebral MRI examination and 1 or more neurological assessment, 9 subjects (23.1%) were observed with new asymptomatic Cerebral Embolic (ACE) lesions. For one of these subjects, an air embolism on sheath insertion was noted during the procedure. 2/9 subjects had interrupted warfarin treatment. All ACE lesions were resolved during follow-up cerebral examination.

All 39 treated subjects underwent a post procedural esophageal endoscopy. No ulceration was observed in any of the cases. Only esophageal erythema was observed in 5 subjects (12.8%).

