#### 8.2.2.2 Study Ablation Procedure Sequence

Subjects will arrive to the electrophysiology laboratory for their ablation procedure and will undergo preparation for the procedure per the hospital’s standard protocol (discretion of investigator)

The AF ablation procedure for this study should follow the below sequence:

- Review CT/MRA to evaluate the number and size of the PV and the left atrial anatomy prior to the ablation procedure
- Transseptal puncture
- Mapping and recording with Lasso® or PentaRay®. Lasso® or PentaRay® to be withdrawn from the left atrium after mapping and recording, prior to insertion of any of the study catheters
- Placement of multi-electrode esophageal temperature monitoring device

- Confirmation of target ACT 350-400 PRIOR to insertion of the Balloon Catheter into the left atrium and maintain throughout the procedure
- Introduction of the RF Balloon Catheter
- Introduction of the Multi-Electrode Circular Diagnostic Catheter (Frontera)
- PV ablation with RF Balloon Catheter and confirmation of isolation by the Frontera
- Confirmation of PV isolation in all targeted PVs using the Frontera
- ROLL-IN SUBJECTS ONLY: Confirmation of PV isolation using Lasso®. Note that use of Lasso® is not allowed for non roll-in subjects.
- ROLL-IN SUBJECTS ONLY: Voltage map creation
- Isoproterenol/Adenosine challenge
- Confirmation of entrance block in all targeted PVs

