### 8.2.2.3 Study Ablation Procedure Guidelines

#### Electrophysiology Study, Mapping and Ablation Procedure

- Anesthesia or sedation should be delivered per standard EP lab procedure.
- Placement of diagnostic catheters:
  - Coronary sinus catheter in the CS for pacing purposes
  - Other catheters may be placed at the discretion of the investigator
- Mandatory use of a multi-electrode esophageal monitoring device to minimize risk of esophageal injury.
- (Optional: Introduce an Intracardiac Echo (ICE) probe to review LA anatomy and PVs)
- Administration of heparin bolus PRIOR to transseptal puncture.
- A single transseptal puncture should be performed per standard EP lab. Aim for an anterior, inferior puncture.
- Following successful transseptal puncture, a FAM map can be performed utilizing Lasso® or PentaRay® (at investigator discretion).
- Confirm target ACT 350-400 sec. Systematic anticoagulation with heparin should be administered with ACT level checked every  $\pm$  15-30 minutes to target ACT of 350-400 seconds throughout the procedure.
- Introduction of the 13.5 F sheath. Before inserting the sheath into the patient, flush the sheath with heparinized normal saline to remove air bubbles. In order to achieve a smooth introduction of the sheath a 10 or 11 F dilator to upsize the femoral vein access before introducing the sheath is recommended.
- Introduce the Balloon Catheter and Frontera Catheter as per instructions for use. To facilitate insertion, the Y-connector (Copilot, Abbot, 0.096 inch) should be used. The choice of loop diameter (15mm, 20mm and 25mm) of the Frontera Catheter is at investigator's discretion. Prior to extending the balloon outside the sheath, advance the Frontera Catheter under fluoroscopy to access the vein
- Use the steerable sheath to drive the Frontera Catheter to the first target vein under fluoroscopy.
- Advance and position the Balloon Catheter at the pulmonary vein ostium.
- Start saline flow rate at 35 mL/min to fully expand balloon.
- Check for occlusion using Radiopaque Contrast (use contrast & saline mixture of 50/50).

- Perform and record angiography to confirm occlusion of the PV (mandatory). Ensure that the catheter is not inside the pulmonary vein before starting ablation.
- Identify the posterior electrodes via the fluoroscopic markers (optional) and on the CARTO image, prior to each ablation.
- When position is satisfactory, commence energy delivery with the Balloon Catheter.

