#### Ablation outside the PV Ostia

- Prophylactic ablation outside the PV or CTI region, empirical sites and CFAE ablation is not allowed per protocol.
- If an arrhythmia requiring ablation outside the PV or CTI region (investigator discretion) is identified, the subject will be excluded from the study before any of the study catheters (Balloon or Frontera) has been inserted.
- If linear lesions for CTI AFL are placed, bidirectional block should be confirmed as demonstrated by mapping and/or pacing maneuvers.

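### Subjects excluded in the EP lab after vascular access or transseptal puncture, but before a study catheter goes in, have no scheduled contact to find later procedural events and enter no analysed safety rate

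*Protocol*

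**What the plan says.** Protocol 4.4 defines excluded subjects by one fact only: "Subjects who are enrolled but never undergo insertion of the study catheter". Their follow-up is limited: "Excluded subjects will only be followed between ICF signature and exclusion for event reporting". The neighbouring category, catheter inserted but no RF delivered, is treated differently: "Discontinued subjects will remain in follow-up for 30 days".

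Invasive steps come before the study catheters. Protocol 8.2.2.2 lists transseptal puncture and then mapping, with "Lasso® or PentaRay® to be withdrawn from the left atrium after mapping and recording, prior to insertion of any of the study catheters". Protocol 8.2.2.3 lists the heparin bolus, transseptal puncture, a discretionary map and then "Introduction of the 13.5 F sheath", all ahead of the balloon and Frontera catheters.

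If an arrhythmia needing ablation outside the PV or CTI region is identified, "the subject will be excluded from the study before any of the study catheters (Balloon or Frontera) has been inserted". Under Protocol 4.3.2, subjects "later found not to be eligible PRIOR to insertion of the study catheter can be replaced".

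The mITT, Safety, Per Protocol, NAE and Roll-In populations all require catheter insertion (Protocol 14.1.1 and 14.1.2; SAP 8.1 and 8.2). The repeat of the primary safety analysis in SAP 11.4.5 uses the Safety Population, and secondary safety in SAP 11.5.1 uses the Safety and mITT populations and the roll-ins.

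**The concern.** The primary safety endpoint counts events within 7 days of the initial mapping and ablation procedure, and it includes tamponade or perforation, stroke, TIA and major access complications or bleeding. Vascular access, transseptal puncture and heparin can cause these, and some appear late. Table 9.1.3-A allows tamponade up to 30 days and has a separate class for diagnosis after discharge.

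A subject who has had those steps and is then excluded has no 7-day or 1-month contact. A subject with the balloon inserted and no RF has 30 days of follow-up, yet has had the same access steps.

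A subject whose procedure is stopped by a complication before the balloon is also excluded by definition, so that event is in no numerator. At stake are the completeness of the procedural safety picture and a safety contact for people who have had an invasive study procedure.

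**Working it through.** **1. The texts side by side.**
- Detection after exclusion: Protocol 4.4 stops event follow-up at exclusion. Protocol 9.4.1 collects adverse events from consent to the end of the study. A site cannot satisfy both. The specific rule in 4.4 is the one it would probably follow, and no visit is scheduled after exclusion.
- Events already known at exclusion: Protocol 4.4 has them reported, and 9.3 has every adverse event followed until resolved. Protocol 4.3.2 follows a subject withdrawn for an AE or SAE until it is resolved or stable. Table 9.4.1-A and 9.4.2 send SAEs and primary AEs to the sponsor within 72 hours. These events are on record.
- Analysis: SAP 11.2 counts excluded subjects in the disposition summary, and SAP 11.3 includes them in the all-enrolled baseline table. No AE listing or rate is planned for them.

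**2. The plan's own design figure.** The test is an exact one-sided 5% binomial test against 15% (SAP 11.4.2). The pass limit c is the largest number of events with P(X ≤ c | n, 0.15) ≤ 0.05. For n = 230, c = 25 (exact alpha 0.044), and power at a true rate of 9.5% is P(X ≤ 25 | 230, 0.095) = 0.797. The SAP Appendix states at least 80%, so the figure reproduces to rounding.

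**3. One uncounted subject with one event, at the limit.** Bounds are exact (Clopper-Pearson) one-sided 95% upper bounds.

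| n | Limit c | Bound at c/n | Bound at (c+1)/(n+1) |
|---|---|---|---|
| 80 | 6 | 14.3% | 7/81: 15.6% |
| 130 | 12 | 14.5% | 13/131: 15.3% |
| 180 | 18 | 14.5% | 19/181: 15.02% |
| 230 | 25 | 14.8% | 26/231: 15.3% |

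At each planned size, a pass exactly at the limit would become a fail.

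**4. Range over an assumed share.** The only exclusion count in the documents is 1 of 40 in the feasibility study (1/40 = 2.5%), before RF, with the stage not given. Assume that lab-excluded subjects make up f = 1%, 2.5% or 5% of the enlarged set, so the number added is m = n·f/(1−f), rounded. The last column gives the events among those m subjects that turn a pass at the limit into a fail.

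| n | m at 1%, 2.5%, 5% | Events needed |
|---|---|---|
| 80 | 1, 2, 4 | 1, 1, 1 |
| 130 | 1, 3, 7 | 1, 1, 2 |
| 180 | 2, 5, 9 | 2, 2, 2 |
| 230 | 2, 6, 12 | 1, 2, 2 |

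**5. Away from the limit.** The SAP Appendix expects 5 to 6 further subjects enrolled during an interim. Starting from 6/85, one added subject with an event gives 7/86, upper bound 14.7%, which still passes. The limit at 85 is 7 events, so 6/85 is already one below it.

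**The case against.** The strongest reply is that analysis sets based on device exposure are a normal choice in a single-arm device study, and that the gap is small. That stands for the primary set, and I would not change it.

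Four stronger readings are tempting, and the documents do not support them.
- **That harm before balloon entry is lost.** A tamponade that stops the procedure begins before exclusion, so it must be reported and followed. It is absent from the rates only.
- **That the feasibility study shows this loss.** Protocol 1.2.3 says that "an air embolism on sheath insertion was noted during the procedure", but that subject was among the 39 with post-ablation MRI, and 39 were treated. Under the present rules the subject would be in the safety set. The single primary event there was diaphragmatic paralysis, so the embolism was not a counted primary event either.
- **That thrombus found on ICE leads to exclusion after transseptal puncture.** Protocol 8.2.2.3 lists optional ICE before heparin and puncture.
- **That a subject excluded on a mapping finding already has the 13.5 F sheath.** Mapping is listed before that sheath, and the map is discretionary. The section on ablation outside the PV ostia does not say that the arrhythmia is found after transseptal access, although the sequence allows it.

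The boundary example is also selective. Stopping at 80 needs a predictive probability above 90%. If 10 to 25 of the 80 are still pending (an assumption), that means at most 4 to 2 observed events, so a final 6/80 would be unusual.

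None of this supplies a contact after exclusion or a planned summary of these subjects' events.

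**Conclusion.** The point holds in a limited form. Protocol 4.4 leaves procedural events that begin after an in-lab exclusion without scheduled detection and conflicts with 9.4.1. No analysed safety rate or planned listing includes any event in these subjects. No stated figure in the plan is wrong because of this.

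The effect on the primary conclusion is probably small. One or two uncounted primary events would change it, under assumed shares of 1% to 5%, and only for a result at the pass limit. The documents give no count of such subjects, so the real size cannot be estimated. The change is worth making because it is cheap and gives these subjects a safety contact.

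**What to change.** - **Protocol 4.4:** split excluded subjects into (a) those excluded before vascular access or transseptal puncture, whose follow-up ends at exclusion as now, and (b) those excluded after either step. For (b), collect AEs and primary AEs at the existing 7-day and 1-month contacts, by phone if preferred. Word this so that 4.4 agrees with 9.3 and 9.4.1.
- **SAP 11.4.5:** add a listing of primary AEs in group (b), and a descriptive sensitivity rate that adds group (b) to the primary safety set. Record any non-study ablation for each subject.
- **Unchanged:** the primary analysis set, hypotheses, alpha and sample size.

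The cost is wording in two documents and one or two contacts for what is likely to be a handful of subjects. The sensitivity rate may be slightly less favourable than the primary one. Some later events may come from a non-study ablation, which is why the listing should record it.

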## 5 Responsibilities

### 5.1 Investigator Responsibilities

Investigators at each participating clinical site will have the following responsibilities:

- Assuring compliance by site personnel with the provisions of the protocol
- Providing the Sponsor with:
  - Signed, dated Investigator Agreement
  - Written EC approval letters and EC-approved consent forms
  - Signed, dated Financial Disclosure form for each participating investigator
  - Curriculum vitae for each investigator
- Maintain an accurate and current Delegation of Authority log which identifies individuals authorized to perform work for the study and assuring compliance by site personnel with the provisions of the protocol
- Completing the appropriate training on the device (ablating investigators only) and the study protocol prior to enrolling and treating subjects
- Maintain accurate and current logs for the study such as:
  - Subject log, Device Accountability Log
- Obtain initial and amendment (if applicable) EC approval and annual review/approval thereafter for the study protocol and informed consent as applicable
- Obtain informed consent form and enroll patients
- Perform medical procedures
- Order tests required by the study protocol
- Review pre-procedure imaging pertaining to the pulmonary vein size prior to treatment
- Follow subjects until the end of the study protocol
- Accurately complete and sign eCRFs in a timely manner
- Maintain relevant source documentation and allow Sponsor direct access to perform monitoring or auditing duties
- Maintain records and provide reports according to prevailing regulatory requirements
- Share relevant study-related information with delegated study staff
- Inform the appropriate entities (e.g., Sponsor, CA, EC) in a timely manner regarding the occurrence of AEs and/or product malfunctions.
- Making sufficient effort to maintain contact with treated subjects who fail to comply with the follow-up requirements
- Maintain study records for at least 5 years or as specified per country specific record retention requirements after the study is completed and or terminated. The Sponsor will notify the Investigator of either of these events.
- Complying with EC and Sponsor annual report requirements, including the final report.

## 5.2 Sponsor Responsibilities

The Sponsor (Biosense Webster, Inc.) will be responsible for the following:

- Conduct of pre-study site assessment and approval
- Preparation and modification (if applicable) of study documents including but not limited to the protocol, CRFs and informed consent
- Selection of appropriately qualified and trained individuals, including monitors, to conduct the study
- Conduct protocol and device training for investigators and research personnel as applicable
- Set-up of study-specific committees.
- Obtain signed study contracts from investigators/hospitals, CROs and other involved parties
- Ship study devices to each site
- Monitor sites for the duration of the study
- Maintain study database
- Inform investigator of his/her responsibilities
- Submit and obtain approval for study from applicable regulatory agencies
- Preparation of reports summarizing the status of the study no less than annually. These reports will be supplied to the Principal Investigator at each site.
- Update Report of Priors, IFU, IB, and Risk Analyses, as applicable
- Update investigators on safety issues, if needed
- Report to study investigators and regulatory agencies, as required
- Have AEs reviewed by the study-specific committees, as required
- Communications with the competent authority
- Submission of any amendments to the Clinical Study Protocol/Investigational Plan to the competent authority.

## 6 Study Device Description

### 6.1 Device Acquisition

After obtaining a fully executed clinical trial agreement and appropriate approvals, the sponsor will initiate shipment(s) of investigational devices to the site. The Sponsor will keep records of all investigational devices shipped to the site. Approved investigational devices will be shipped directly to the site and will be received by the site. Investigators are responsible for appropriate logging of the devices received, verification of packing slip information (i.e., lot numbers and quantity shipped), date and identity that each device was used in the study, disposition information regarding disposal or return to the Sponsor.

## 6.2 Device Storage and Stability

Devices are to be stored in a secure/locked location and in accordance with the IFU. Do not use this device after the "Use By" date.

## 6.3 Device Preparation

Information related to device preparation can be found in the Instruction for Use.

## 6.4 Instructions for Use

A comprehensive set of IFU for the Study Devices, Generator, and all accessory cables/interface cables is contained in each product package and is also available upon request.

## 6.5 Device Description and Specific Considerations

[figure not shown]
[REDACTED]

[REDACTED]

[REDACTED]

[REDACTED]

[REDACTED]

[Redacted line of text]

[Redacted block of text consisting of seven lines]

[Redacted block of text consisting of five lines]

[Redacted block of text consisting of seven lines]

[Redacted block of text consisting of two lines]

[REDACTED]

- [REDACTED]
- [REDACTED]
- [REDACTED]
- [REDACTED]
- [REDACTED]
- [REDACTED]
- [REDACTED]
- [REDACTED]
- [REDACTED]
- [REDACTED]

[REDACTED]

[figure not shown]
- [REDACTED]
- [REDACTED]
- [REDACTED]
- [REDACTED]
- [REDACTED]
- [REDACTED]
- [REDACTED]
- [REDACTED]
- [REDACTED]
- [REDACTED]
- [REDACTED]

[REDACTED]

[REDACTED]

[REDACTED]

## 7 Study Medication

The following medications are applicable for this protocol:

- **PRIOR to the procedure**
  - Uninterrupted anticoagulation therapy should be in place at least 1 month prior to ablation procedure
  - If receiving warfarin/coumadin therapy, subjects must be maintained on warfarin/coumadin for at least 3 weeks prior to treatment with an INR  $\geq 2$  (to be confirmed maximum 48h hours pre-procedure). Any INR  $<2$  within 3 weeks prior to ablation will lead to exclusion of the patient or postponement of the study procedure.
  - Anticoagulation therapy should not be interrupted or stopped prior to the procedure (this means no doses should be missed or omitted) and daily regimen should be continued.
  - AAD therapy should be managed as per the institution's standard of care
  
- **DURING the procedure**
  - Administer a heparin bolus PRIOR to transeptal puncture.
  - Target an ACT of 350-400 seconds prior to inserting the balloon and throughout the procedure.
    - ACT levels **MUST** be checked every  $\pm 15-30$  minutes during the procedure to ensure an ACT target of 350-400. All recordings (ACT level, timing of heparin administration and dose) must be documented in the medical records as source documentation.
  - Flush all tubing and sheath continuously with heparinized saline.
  
- **FOLLOWING the procedure**
  - Anticoagulation therapy is strongly recommended for at least 2 months following ablation.
  - Additional medications needed to treat clinical indications are at the discretion of the clinical investigation physician.
  - AAD management during the study will be at the discretion of the investigator

